## **7.4 Safety/Potential Adverse Events/Protection Against Risk**

The risks to the patient are limited to the minor risk of performing venipuncture and the risk of rejection with TAC-WD. The National Cancer Institute Common Terminology Criteria for Adverse Events v3.0 (CTCAE), dated December 12, 2003 will be used to grade all adverse (either serious or non-serious) events. It is the responsibility of the Principal Investigator to oversee the safety of the study. This safety monitoring will include careful assessment and appropriate reporting of adverse events as noted above. Medical monitoring will include a regular assessment of the number and type of serious adverse events. Information on all adverse events (signs, symptoms, abnormal diagnostic procedures, treatments) will be recorded in the appropriate adverse event module of the case report form (CRF). The clinical course of each event will be followed until resolution, stabilization, or until it has been determined that the study participation is not the cause. Serious adverse events that are still ongoing at the end of the study period will be followed to determine the final outcome.

Reports of all serious adverse events (including follow-up) will be submitted to the IRB within 24 hours of the investigator's knowledge of the event. Follow-up reports will be submitted to the IRB within 10 working days. The IRB/Office for the Protection of Research Subjects at NU is under the direction of [name]- [contact]. As this is a prospective study using primary data collection with a drug of interest all adverse events (AEs) – including serious adverse events (SAEs) and safety endpoints (where relevant) – will be collected and recorded in the study and safety database, irrespective of causal association. All adverse reactions identified will be reported to the local Health Authority in accordance with national regulatory requirements.

All of the risks and benefits will be discussed with the patient at the time of informed consent. The patient will undergo informed consent prior to all liver biopsies and suspected rejection will be managed as per our standard of care (SOC). The biopsies will be performed using a 16-18 Gauge BioPince® biopsy instrument, which utilizes a Tri-axial "Cut and Capture" cannula system. We will remove a 0.5-1 cm biopsy piece from the main 3 cm sample for genomic analysis. Thus, only one pass liver biopsy is required per SOC and not extra for the study. The patient will be monitored for 2 hours after each liver biopsy in the Procedure Unit at Northwestern. Vital signs will be performed before and every 15 minutes x 1 hour, every 30 minutes x 1 hour per standard protocol. Any atypical symptom after biopsy, i.e. shortness of breath, hypotension, tachycardia, fever, severe abdominal pain, will be investigated immediately by the physician performing the biopsy.

The patient will be monitored for any complication of this study as he/she would as part of our standard management, i.e. monitoring of graft function, kidney function, trough IS levels, cholesterol levels, urine protein/creatinine ratio. This follows the clinical practice that has been occurring at our center over the last 20 years. There is a risk of rejection with TAC-WD (~20%) which will be discussed with the patient. If a graft loss occurs due to the study protocol or  $\geq 30\%$  rejection occurs with TAC-WD, the study will be terminated for safety reasons. This is counterbalanced by the equipoise of the potential for preservation of renal function and other TAC side effects by TAC-WD. The blood collection will occur at the time of the standard of care blood tests after transplantation and thus will not add additional venipuncture risk. The allowed amount of blood per venipuncture/day will not be exceeded according to our IRB rules. Overall, the patient will be well informed of our standard of care approaches and research protocols, with appropriate discussion and consent.

Another risk involves breach of patient confidentiality during the study. To avoid this, all informed consents, medical records, and electronic databases will be stored in a locked location at Northwestern, with access limited to study personnel. Patient samples utilized for research will be de-identified by a coding system only accessed by the Co-PIs. Special procedures for ensuring patient confidentiality will be implemented in accordance with the HIPAA. Data transmission and the distributed data systems will have multiple layers of security. Each study subject will be assigned a unique identification number. Only this number will be used to identify subjects in any individual tabulation. It is expected that only group data will be published. If individual subject data are to be published, no identifying information will be included. The study files will be maintained in a secure location. Access to computerized data will be restricted to study personnel. Password authentication will be enforced. These passwords will be changed on a quarterly basis and whenever the Database Administrator makes a determination for a security change.

#### **7.4.1 Physical examination**

On visits 3, 4, 5, 7 and early termination an exam will be performed.

#### **7.4.2 Vital signs**

Vital signs including blood pressure, pulse, respiratory rate and temperature will be taken at every SOC visit and study-related visit when the subjects come to clinic.

#### **7.4.3 Height and weight**

Subjects will be weighed at every visit and their height will be taken at the first study visit.

#### **7.4.4 Laboratory evaluations**

At liver transplant donor/recipient collection of lymph nodes and liver biopsy tissue will take place if the patient is consented prior to transplantation. Liver biopsy tissue will also be collected at the time of a suspected rejection.

Blood samples for flow cytometry, PBMCs, RNA and sera will be collected at visits 3, 4, 5, 6, 7 and rejection.

Standard SOC laboratory tests will be performed per our transplant center post-LT protocol: CBC, CMP, trough IS levels three times weekly (0-1 month post-LT), two times weekly (1-3 months post-LT), one time weekly (3-6 months post-LT).

#### **7.4.5      Pregnancy and assessments of fertility**

##### **Pregnancy**

There are no adequate and well-controlled studies of Zortress in pregnant women. In rats and rabbits, everolimus crossed the placenta and was toxic to the conceptus. The potential risk for humans is unknown. Zortress should be given to pregnant women only if the potential benefit to the mother justifies the potential risk to the fetus. Women of childbearing potential should be advised to use effective contraception methods while they are receiving Zortress and up to 8 weeks after treatment has been stopped.

##### **Nursing Mothers**

It is not known whether everolimus is excreted in human milk. Everolimus and/or its metabolites readily transferred into milk of lactating rats at a concentration 3.5 times higher than in maternal serum. Because many drugs are excreted in human milk and because of the potential for serious adverse reactions in nursing infants from everolimus, women should avoid breast-feeding during treatment with Zortress.

#### **7.4.6      Appropriateness of safety measurements**

All safety measurements are appropriate as standard of care for patient management and this protocol.

#### **7.4.7      Other biomarkers**

Please see Exploratory Objectives above

### **8              Safety monitoring**

It is the responsibility of the Principal Investigator and sub-investigators to oversee the safety of the study at their site. This safety monitoring will include careful assessment and appropriate reporting of adverse events as noted above. Medical monitoring will include a regular assessment of the number and type of serious adverse events.

## 8.1 Adverse events

**Definition of an AE:** Any untoward medical occurrence in a subject administered a pharmaceutical product that does not necessarily have a causal relationship with the treatment. An AE can therefore be any unfavorable and unintended sign (including an abnormal laboratory finding), symptom, or disease temporally associated with the use of a medicinal (investigational) product, whether or not considered related to the investigational medicinal product. Investigational Medicinal Product (IMP) includes the drug under evaluation and the comparator drug(s) if specified as part of the research objective, given at any time during the study. Medical conditions/diseases present before starting the drug of interest are only considered adverse events if they worsen after starting the drug of interest.

The occurrence of adverse events will be sought by non-directive questioning of the patient at each visit during the study. Adverse events also may be detected when they are volunteered by the patient during or between visits or through physical examination, laboratory test, or other assessments. All adverse events will be recorded in the study database including the following information:

1. the severity grade (mild, moderate, severe) or (grade 1-4)
2. its relationship to the drug(s) of interest (suspected/not suspected)
3. its duration (start and end dates or if continuing at final exam)
4. whether it constitutes a serious adverse event (SAE)

## 8.2 Serious adverse event reporting

**An SAE:** is any untoward medical occurrence that at any dose:

- results in death,
- is life-threatening,
- requires inpatient hospitalization or prolongation of existing hospitalization,
- results in persistent or significant disability/incapacity,
- is a congenital anomaly/birth defect,
- is otherwise a significant medical event.

This includes any SAEs likely to arise from the trial indication or progression of underlying/concomitant illness (es) (e.g. progression of cancer in oncology trials), unless specified in the protocol as study specific exemptions.

Any SAE, irrespective of causality, occurring after the subject has provided informed consent and until four weeks after the subject has stopped study participation must be reported unless otherwise stated in the protocol. SAEs occurring after four weeks from ending study participation should only be reported if considered by the Investigator attributable to the exposure to the investigational drug(s) during the trial period. This includes the period in which the study protocol interferes with the standard medical treatment given to a subject, even if study treatment has not yet started (e.g. withdrawal of previous treatment during washout period, change in treatment to a fixed dose of concomitant medication).

**Timelines:** All serious adverse events (SAEs) from interventional clinical trials must be reported by the sites to Sponsor within 24 hours of occurrence of the SAE. The timelines for investigator initiated trials reporting to Novartis will be done as per Third Party Study/Investigator Initiated Trial Agreement.

**Follow-up reports:**

SAEs will be followed until resolution or until it is judged to be permanent, and an assessment will be made at each visit (or more frequently, if necessary) of any changes in severity, the suspected relationship to the drug of interest, the interventions required to treat it, and the outcome.

The Sponsor shall support Novartis in the following-up of all SAEs so that complete information is available to maintain patient safety and also as part of any commitments by Novartis to any Health authority OR specific Health authority follow-up requests for the product under investigation.

### **8.3      Pregnancies**

To ensure patient safety, each pregnancy in a patient (or a patient's partner) on study drug must be reported to Novartis within 24 hours of learning of its occurrence. The pregnancy will be followed up to determine outcome, including spontaneous or voluntary termination, details of the birth, and the presence or absence of any birth defects, congenital abnormalities, or maternal and/or newborn complications.

## **9       Data review and database management**

### **9.1      Data collection (data handling and record keeping)**

This study is to be conducted according to US and international standards of Good Clinical Practice (FDA Title 21 part 312 and International Conference on Harmonization guidelines), applicable government regulations and Institutional research policies and procedures. This protocol and any amendments will be submitted to the Northwestern University Institutional Review Board (NU IRB), for formal approval of the study conduct.

Information about study subjects will be kept confidential and managed according to the requirements of the Health Insurance Portability and Accountability Act of 1996 (HIPAA).

**Consent:**

All subjects for this study will be provided with a printed consent form describing this study and providing sufficient information for subjects to make an informed decision about their participation in this study. This consent form will be submitted with the protocol for review and approval by the NU IRB for the study. The formal consent of a subject, using the NU IRB-approved consent form, will be obtained before the subject is submitted to any study procedures. This consent form will be signed by the subject and the investigator-designated research professional obtaining the consent. The subject will be given a signed copy of the informed consent for their records.

**Source Documents:**

Source data is all information, original records of clinical findings, observations, or other activities in a clinical trial necessary for the reconstruction and evaluation of the trial. Source data are contained in source documents. Examples of these original documents, and data records include, but are not limited to: hospital records, clinical and office charts, laboratory notes, memoranda, subjects' diaries or evaluation checklists, pharmacy dispensing records, recorded data from automated instruments, copies or transcriptions certified after verification as being accurate and complete, microfiches, photographic negatives, microfilm or magnetic media, x-rays, subject files, and records kept at the pharmacy, at the laboratories, and at medico-technical departments involved in the clinical trial.

**Confidentiality:**

Information about study subjects will be kept confidential and managed according to the requirements of the Health Insurance Portability and Accountability Act of 1996 (HIPAA). Those regulations require a signed subject authorization (which is incorporated into a single document which includes the Northwestern University Informed Consent Form). This combination document must inform the subject of the following:

- What protected health information (PHI) will be collected from subjects in this study
- Who will have access to that information and why
- Who will use or disclose that information
- The rights of a research subject to revoke their authorization for use of their PHI.

In the event that a subject revokes authorization to collect or use PHI, the investigator, by regulation, retains the ability to use all information collected prior to the revocation of subject authorization. For subjects that have revoked authorization to collect or use PHI, attempts should be made to obtain permission to collect at least vital status (i.e. that the subject is alive) at the end of their scheduled study period.

## **9.2 Database management and quality control**

**Case Report Forms:**

After study initiation, the electronic case report form (eCRF) will be the primary data collection instrument for the study. Only the Investigators will have access to this password protected file. No subject identifiers will be included in the eCRF and electronic databases that are used to record clinical data on patients. All clinical data will be kept completely confidential.

**Auditing and Inspecting:**

The investigator will permit study-related monitoring, audits, and inspections by the NU IRB, the sponsor, government regulatory bodies, and University compliance and quality assurance groups of all study related documents (e.g. source documents, regulatory documents, data collection instruments, study data etc.). The investigator will ensure the capability for inspections of applicable study-related facilities (e.g. pharmacy, diagnostic laboratory, etc.).

Participation as an investigator in this study implies acceptance of potential inspection by government regulatory authorities and applicable University compliance and quality assurance offices.

**Record Retention:**

It is the investigator's responsibility to retain study essential documents on site for at least 2 years after the study has been formally terminated at the NU IRB. After this time, it is up to the investigator to determine whether the documents should be stored off-site at O'Hare Records, located in Rosemont, IL for up to 13 more years. Once the investigator determines how long to keep the records, when that time frame is up it is the responsibility of the investigator to ensure that all study records are properly disposed of by shredding.

## **10 Data analysis**

### **10.1 Populations for analysis**

Since there is no randomization in the study, the groups that are analyzed are those that have rejection before TAC-WD, those who develop rejection during/after TAC-WD, and those who never have rejection before or after TAC-WD.

### **10.2 Analysis of the primary objective(s)**

Primary objective: To identify cellular and molecular metrics of immune regulation that may predict successful TAC withdrawal in favor of EVL early after LT.

Overall Strategy and Rationale: The objective is to test the working hypothesis that, in a prospective study, cellular and genomic markers of immunoregulation become more pronounced after early rejection-free TAC-WD/EVL compared to failed (rejection) TAC-WD. Conversely, if these markers do not signify immunoregulation, we hypothesize that TAC-WD/EVL will not be successful (i.e. rejection will ensue requiring reinstatement of TAC). The rationale is that the immunoregulatory mechanisms of IS therapy (EVL vs. CNI) can be more adequately clarified and that a higher % of patients can undergo successful TAC-WD/EVL by utilizing these serial, safe blood biomarkers to predict rejection, before it occurs, i.e. by comparing these signals right before and after TAC-WD. Our hypothesis is based on our previous observations that late mTOR-I conversion increased % of Treg/DCreg in blood/tissue sites and generated immunoregulatory proteogenomic signatures and that AR can be diagnosed in the peripheral blood by genomic microarrays. Therefore, the plan is to perform sequential flow cytometry immunophenotyping and genomic signature analysis in the blood before, during and after attempted TAC-WD/EVL.

Studies Planned and Methods:

i) Blood Immunophenotyping. The approach will be to conduct flow cytometry immunophenotyping of peripheral blood before TAC-WD initiation (1 to 2 months and 3 months ( $\pm$  1 month)), right at total TAC-WD (4 months ( $\pm$  1 month)), 2 weeks after full TAC-WD (4.5 months ( $\pm$  1 month)) and study end (6 months ( $\pm$  1 month)) post-LT to analyze cellular changes. Methods: The Immune Monitoring Laboratory at NU (Co-Director [name]) will perform the immunophenotyping. PBMC are isolated from heparinized 30 cc samples on Ficoll-Hypaque gradients. Surface markers are detected with monoclonal antibodies for the T cell subsets CD3, CD4, CD8, CD25, CD45RA, CTLA4 and CD127 followed by fixation/permeabilization/incubation with human FOXP3 antibodies and final flow cytometric analysis. RBC-lysed peripheral blood is also labeled with monoclonal antibodies for T cell subsets, naïve/memory/regulatory B cells (CD19, CD27, IgD, IgM, IL-6), monocytes (CD14) and NK cells (CD56) to quantify the absolute cell numbers per  $\mu$ L. In addition, dendritic cell surface markers are analyzed as follows: monocyteoid vs. plasmacytoid (CD11c; CD123) ratio; antigen processing markers (CD83; CD205); markers inducing Tregs (ILT3; ILT4). For statistical analysis, we perform within subject comparisons on PBMC for both successful and failed TAC-WD/EVL groups using appropriate paired analysis (paired t-test or Wilcoxon Signed Rank test). For the main hypothesis testing, repeated measures of analysis of variance (RM-ANOVA) are used to test the trajectory variations between the groups on PBMC over time. Two-sided F-test statistics are applied;  $\alpha=0.05$  (stats by NU Transplant Statistician).

ii) Gene Expression Microarrays: The approach will be to conduct parallel serial genomic bioassays of peripheral blood before and after attempted TAC-WD/EVL (same time points as immunophenotyping). Methods: The Genomics Core at Scripps Clinic (Director, [name]) will perform the microarray analysis. Blood will be collected in PaxGene tubes and sent to Scripps for the gene microarrays. Affymetrix® Hu133 Plus Peg microarrays will be used to test for differentially expressed genes between those developing AR vs. without AR during TAC WD. We will also perform biological function and canonical pathway mapping of several immune/inflammatory gene pathways. For statistical analysis, we report for each mRNA and microRNA comparison the T-test p-value, its non-parametric analog (Kruskal Wallis test), the fold change, and for multi-analyte signatures, the area under the receiver operating curve (concordance index/C-index) and q-values by member genes/proteins. We then calculate the predictive accuracy, sensitivity and specificity of each signature (statistics by [name] informatics group at Scripps Clinic)

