## 3 Objectives

**Primary Objective:** To identify cellular and genomic metrics of immune regulation that may predict successful TAC withdrawal in favor of EVL early after LT.

*It is our hypothesis that these markers of immunoregulation are more pronounced with successful (no rejection) vs. unsuccessful (rejection) TAC-WD/EVL.* The approach will be to analyze the peripheral blood for phenotypic Tregs correlating with mRNA footprints of regulation. These analyses will be performed in a prospective pilot clinical trial of LT recipients on standard combination TAC and EVL at 1 to 2 months post-LT selected to undergo TAC-WD/continued EVL at 3-4 months ( $\pm$  1 month). Thus, based on the clinical trials, we expect rejection to occur in 20% in the 1-2 month period following TAC-WD/EVL and that this will be predicted by bioassays analyzed prior to and/or immediately after full TAC-WD. Alternatively, we expect 80% to not experience rejection with TAC-WD/EVL and that this will be predicted by bioassays analyzed prior to and/or right after full TAC-WD. Therefore, the use of these assays would eventually serve to detect and predict appropriate candidates for successful early TAC-WD/EVL, enhancing the use of EVL in LT and allowing patients to be spared of CNI toxicity past the first 3-4 months following LT.

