### 10.3.3 Biomarkers/Studies Planned

*i) Blood Immunophenotyping.* The approach will be to conduct flow cytometry immunophenotyping of peripheral blood before TAC-WD initiation (3 months ( $\pm$  1 month)), right at total TAC-WD (4 months ( $\pm$  1 month)), 2 weeks after full TAC-WD (4.5 months ( $\pm$  1 month)) and study end (6 months ( $\pm$  1 month)) post-LT to analyze cellular changes. Methods : The Immune Monitoring Laboratory at NU (Co-Director [name]) will perform the immunophenotyping. PBMC are isolated from heparinized 30 cc samples on Ficoll-Hypaque gradients. Surface markers are detected with monoclonal antibodies for the T cell subsets CD3, CD4, CD8, CD25, CD45RA, CTLA4 and CD127 followed by fixation/permeabilization/incubation with human FOXP3 antibodies and final flow cytometric analysis. RBC-lysed peripheral blood is also labeled with monoclonal antibodies for T cell subsets, naïve/memory/regulatory B cells (CD19, CD27, IgD, IgM, IL-6), monocytes (CD14) and NK cells (CD56) to quantify the absolute cell numbers per  $\mu$ L. In addition, dendritic cell surface markers are analyzed as follows: monocyteoid vs. plasmacytoid (CD11c; CD123) ratio; antigen processing markers (CD83; CD205); markers inducing Tregs (ILT3; ILT4). For statistical analysis, we perform within subject comparisons on PBMC for both successful and failed TAC-WD/EVL groups using appropriate paired analysis (paired t-test or Wilcoxon Signed Rank test). For the main hypothesis testing, repeated measures of analysis of variance (RM-ANOVA) are used to test the trajectory variations between the groups on PBMC over time. Two-sided F-test statistics are applied;  $\alpha=0.05$  (stats by NU Transplant Statistician).

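### The main flow-cytometry test compares trajectories, so no defined analysis assesses whether a pre-withdrawal Treg% predicts rejection

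*Combined protocol and SAP*

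**What the plan says.** Section 3 sets the primary objective as finding cellular and genomic measures that may predict successful tacrolimus (TAC) withdrawal. Of rejection after withdrawal it says that "this will be predicted by bioassays analyzed prior to and/or immediately after full TAC-WD". Section 3.1 makes Treg% (or other regulatory cells) and the mRNA rejection signatures joint parts of the primary endpoint.

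For the flow half, section 10.2 i) plans two analyses. One is "within subject comparisons on PBMC for both successful and failed TAC-WD/EVL groups using appropriate paired analysis", which looks at change inside each outcome group. The other is declared as the main test: "main hypothesis testing, repeated measures of analysis of variance (RM-ANOVA) are used to test the trajectory variations between the groups on PBMC over time". Its alpha is 0.05, and "Two-sided F-test statistics are applied". Section 10.3.3 i) repeats that the purpose is to "test the trajectory variations between the groups on PBMC over time". Neither section says which RM-ANOVA effect is meant, and neither gives an AUC, sensitivity or specificity for any flow marker.

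For the genomic half, section 10.2 ii) plans a comparison of patients with and without acute rejection (AR) and an AUC for multi-analyte signatures, and adds: "We then calculate the predictive accuracy, sensitivity and specificity of each signature".

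Section 4 also promises that the blood biomarkers will be compared between AR and no-AR patients, but names no test and no visit.

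**The concern.** A test of trajectory variations is most naturally read as the group-by-time interaction: do the two outcome groups' curves differ in shape? Prediction asks something else: does the value in hand before TAC is withdrawn separate patients who will reject from those who will not? A marker that is lower in future rejecters by a steady amount at every visit would be useful for choosing candidates, yet it gives parallel curves and no interaction. Conversely, curves that separate only once TAC is gone give an interaction without any pre-withdrawal information.

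One of the two uses named in section 2 is selecting candidates for withdrawal, and section 3.3 branches on whether the markers prove predictive. At stake is whether the flow half of the primary endpoint can be judged predictive or not by a defined analysis.

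**Working it through.** The documents give no power, effect size, SD or within-patient correlation, so there is no planned figure to reproduce.

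**Inputs from the documents.** Of 20 patients starting withdrawal, section 10.4 expects 4-5 with AR and 14-15 without. Figure 6 gives 15 v 5. The 20% rate in section 3 gives 0.20 × 20 = 4, so 16 v 4. Alpha is 0.05, two-sided. Four flow visits are planned (months 3, 4, 4.5 and 6). Section 10.2 adds a month 1-2 sample, but Table 7-1 marks it as unfunded and not mandatory.

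**Assumptions.** Compound symmetry, complete data, correlation ρ from 0.3 to 0.7, and group differences d from 1.0 to 2.0 SD.

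**1. Constant difference.** If the group difference is d at every visit, each visit's difference minus the average over visits is d − d = 0. That is exactly the null of the interaction test, so its rejection rate is alpha for any d, ρ or group size. Simulation (20,000 runs per case) gave 4.8-5.4% in all 54 combinations of three group splits, four or five visits, three values of ρ and three of d.

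**2. Difference that changes over time.** Interaction power, 15 v 5, for d = 1.0 / 1.5 / 2.0 SD:

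| Pattern | ρ = 0.3 | ρ = 0.5 | ρ = 0.7 |
|---|---|---|---|
| Present at month 3, grows from d to 2d | 26 / 54 / 81% | 35 / 69 / 92% | 56 / 91 / 99.6% |
| Present at month 3, vanishes after withdrawal | 43 / 81 / 97% | 59 / 93 / 99.7% | 82 / 99 / >99% |
| Absent at month 1-2, present from month 3 (five visits) | 32 / 66 / 91% | 44 / 82 / 98% | 69 / 97 / >99% |
| Absent at month 3, appears during or after withdrawal | 31 / 63 / 89% | 42 / 80 / 97% | 66 / 96 / 99.9% |

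The last row carries no month-3 information, yet its power is much the same as in the other rows. A significant interaction therefore does not identify a predictor.

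**3. Direct comparison at month 3.** Under normality d = √2 × z(AUC). For AUC 0.80, d = 1.414 × 0.842 = 1.19; for AUC 0.89, d = 1.73. The noncentrality is d × √(n1·n2/(n1+n2)). For 15 v 5 and AUC 0.80 this is 1.19 × √3.75 = 2.30 on 18 df (critical value 2.10), giving 59% power. For 16 v 4 it is 1.19 × √3.2 = 2.13, giving 52%. At AUC 0.89 the powers are 89% and 84%.

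**4. RM-ANOVA group effect.** The variance of a four-visit mean is (1 + 3ρ)/4, which is 0.70 at ρ = 0.6. For a constant d = 1.19, the standardised difference is 1.19/√0.70 = 1.42 and the noncentrality is 1.42 × √3.75 = 2.75, giving 74% power. Over ρ = 0.3 to 0.7 the range is 89% to 70%.

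**5. Precision of an AUC.** Hanley-McNeil variance at AUC 0.80, 5 v 15: Q1 = 0.80/1.20 = 0.667 and Q2 = 2 × 0.64/1.80 = 0.711. The variance is [0.16 + 4 × (0.667 − 0.64) + 14 × (0.711 − 0.64)]/75 = 0.0168, so SE = 0.13. The 95% interval runs from about 0.55 to the upper bound of 1.

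Missing data would make the trajectory test worse than shown: section 7.3 and Table 7-1 end a patient's study at rejection, so rejecters may lack later samples. The month-3 sample is taken at the visit where withdrawal starts, so it should exist for everyone who begins.

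**The case against.** The strongest reply is that the working hypothesis in section 10.2 is itself about change: markers should become more marked after rejection-free withdrawal than after failed withdrawal. It also speaks of comparing signals just before and just after withdrawal, and section 3 counts assays immediately after full withdrawal as predictive. Section 3.3 foresees serial signals guiding whether withdrawal continues. A trajectory test speaks to all of that. This stands, and it is a reason to keep the RM-ANOVA.

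Second, RM-ANOVA also produces a group effect. For a constant difference with complete data, that effect beats the single-visit test (74% against 59% in steps 3 and 4). This stands too, but the plan does not name that effect. It also averages in samples drawn at and after TAC stop, so it would not show that the pre-withdrawal value alone separates the groups.

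Third, section 4 does promise an AR v no-AR comparison. The gap is therefore one of specification, since that sentence gives neither test nor visit.

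Fourth, this is a pilot without a power claim. That excuses low power. It does not supply the missing analysis.

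A reader might go further and infer that the plan cannot answer its primary objective. The documents do not support this: the change hypothesis is addressed, and the genomic half has group comparisons, AUC, sensitivity and specificity. Nor does a missed Treg% by itself redirect the programme. Item 2 of section 3.3 applies when the immunophenotypic and the genomic markers both fail; item 1 is met if either succeeds.

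**Conclusion.** The point holds in a limited form. The declared main flow test does not assess prediction from a pre-withdrawal sample, and no other flow analysis is specified that does. For a constant group difference the interaction test has power equal to alpha, 5%; this follows from the definition of the test and needs no assumed SD, effect size or correlation. It would be wrong to extend the 5% to every marker that already differs before withdrawal. Where the difference changes over time, power was 26% to over 99% across the assumed ranges, but the result cannot separate a predictor from a later divergence. The power figures for changing differences, the month-3 comparison and the group effect all rest on assumed effect sizes, compound symmetry and complete data.

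**What to change.** In 10.2 i) and 10.3.3 i), add a pre-specified analysis along these lines: Treg% at Visit 4 (month 3, before the withdrawal reductions start) is compared between patients who later reject and those who do not, reporting the AUC with a 95% CI and a permutation or Welch p-value. Repeat it at Visits 5 and 6 among patients still rejection-free at that draw, counting only rejections that occur afterwards.

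Keep the RM-ANOVA for the hypothesis about change, and state whether the group-by-time effect, the group effect or both will be tested. It need not lose its place as the main test of that hypothesis. Tie the general AR v no-AR sentence in section 4 to the new analysis.

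The cost is rewording and a few more estimates from the same samples and assays. With 4-5 expected rejecters the intervals will be wide (step 5), and wider at Visits 5 and 6 if some rejections have already occurred. The report should present these as estimates for planning the larger trial.
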